3.1 Description of the Study

This is an open-label, nonrandomized, Phase 1/Phase 2 study to determine the safety and tolerability, define the MTD or PAD, and to assess the preliminary efficacy of NC762 in subjects

with advanced or metastatic solid tumors. Subjects will receive NC762 on Day 1 of each cycle. Phase 1 of the study will begin with 14-day cycles; however, alternate dose administration schedules may also be explored depending on PK, PD, biomarker, safety results, and feedback from investigators. The study will be conducted in 2 parts:

- Phase 1 – Dose Escalation (Phase 1a) and Safety Expansion (Phase 1b) will determine the MTD and/or the PAD, defined as a dose that provides a maximal biochemical effect, or an increase in biomarkers of immune activity. It will also define the optimal dose administration schedule and the maximum number of tolerated doses (MNTD).
- Phase 2 – Dose Expansion will evaluate the recommended dose and administration schedule determined in Phase 1 in subjects with advanced or metastatic non-small cell lung (squamous cell), hepatocellular carcinoma, HER2+ breast, and ovarian cancer, or other tumor type as identified with emerging data.

Figure 1: Study Design

RR: Response Rate (ORR) per RECIST v1.1

3.1.1 Phase 1

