4.2 Subject Exclusion Criteria

A subject who meets any of the following criteria will be excluded from the study:

- 1) Inability to comprehend or unwilling to sign the ICF.
- 2) Laboratory and medical history parameters not within the protocol-defined range.
 - a. Absolute neutrophil count $< 1.5 \times 10^9/L$.
 - b. Platelets $< 100 \times 10^9/L$.
 - c. Hemoglobin $< 9 \text{ g/dL}$ or $< 5.6 \text{ mmol/L}$.
 - d. Serum creatinine $> 1.5 \times$ institutional upper limit of normal (ULN) *or* calculated creatinine clearance $< 50 \text{ mL/min}$ (using Cockcroft-Gault formula)
 - e. Aspartate aminotransferase (AST) and alanine aminotransferase (ALT) $\geq 2.5 \times$ ULN with the following exceptions: Subjects with documented liver metastases AST and/or ALT $\leq 5 \times$ ULN. Patients with documented liver or bone metastases: alkaline phosphatase $\leq 5 \times$ ULN.
 - f. Total bilirubin $\geq 1.5 \times$ ULN.
Note: Subjects with documented Gilbert's syndrome with elevated total bilirubin may be permitted to enroll after consultation with the medical monitor.
 - g. International normalized ratio (INR)/prothrombin time (PT) $> 1.5 \times$ ULN *or* Activated partial thromboplastin time (aPTT) $> 1.5 \times$ ULN, except for subjects receiving therapeutic anticoagulation.
- 3) Transfusion of blood products (including platelets or red blood cells) or administration of colony-stimulating factors (including granulocyte colony-stimulating factor, granulocyte macrophage colony-stimulating factor, or recombinant erythropoietin) within 7 days before the first administration of study drug.
- 4) Receipt of anticancer medications or investigational drugs within the following intervals before the first administration of study drug:
 - a. ≤ 14 days for chemotherapy, targeted small molecule therapy, hormonal therapy or radiation therapy.
Note: Subjects must not have had radiation pneumonitis because of a treatment.
Note: A 1-week washout is permitted for palliative radiation to non-central nervous system (CNS) disease with medical monitor approval.
Note: Bisphosphonates and denosumab are permitted medications; continuation of hormonal therapy is allowed for CRPC patients.
 - b. ≤ 28 days for prior immunotherapy or persistence of active cellular therapy (e.g., chimeric antigen receptor T cell therapy; other cellular therapies must be discussed with the medical monitor to determine eligibility).

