
• \geq Grade 2 ocular irAEs• Grade 3 irAEs that do not improve to baseline or at least Grade 1 in < 5 days with appropriate care or with corticosteroid therapy• Grade 4 irAEs regardless of duration.

General

- Inability to receive the planned number of doses within the 28-day DLT period due to toxicity, regardless of grade, will be considered a DLT.
- Combined elevations in serum ALT >3 times the upper limit of normal (ULN) **and** bilirubin >2 ULN in the absence of alkaline phosphatase (ALP) elevation (<2 ULN)
 - Abnormal liver function tests as indicated by the criteria above will be considered a DLT if no other reason can be found to explain the combination of increased liver markers such as viral hepatitis A, B, or C; preexisting or acute liver disease; or another drug capable of causing the observed injury.
- Any death not clearly due to the underlying disease or extraneous causes.

MTD

- In Phase 1 of the study, the MTD will be defined as 1 dose level below that at which \geq one-third of subjects in a cohort have DLTs.
- In Phase 2 of the study, toxicities will continue to be monitored. If the cumulative incidence of DLTs occurs in > 33% of subjects after 6 subjects have been observed for at least 28 days, then further enrollment may be interrupted, and the investigators and sponsor will meet and reassess the MTD. All AEs, regardless of the time of occurrence on study, may be considered in determining the appropriate dose, schedule, and MNTD.

MNTD

- Throughout the treatment period, if > 33% of subjects (minimum of 6 subjects) experience a \geq Grade 3 toxicity related to study drug after completing \geq 4 cycles, then dose administration will be stopped, and the MNTD will be determined in conjunction with the investigators and sponsor based on all available safety data.

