5.4.6 Criteria and Procedures for Dose Interruptions and Adjustments of Study Drug

Treatment with study drug may be delayed allowing for resolution of toxicity. Subjects may resume treatment if no medical condition or other circumstance exists that, in the opinion of the investigator, would make the subject unsuitable for further participation in the study. For toxicities that occur outside of the 28-day DLT period, the treating investigator should contact the medical monitor to discuss the case of any subject whose treatment has been delayed for more than 4 weeks (28 days). **Note:** Patients who have >28-day treatment delay must discontinue from further treatment.

Instructions for dose modifications and interruptions are outlined in Table 4. Individual decisions regarding dose interruptions and reductions should be made using appropriate clinical judgment in consultation with the medical monitor, considering relatedness of the AE to the study drug and the subject's underlying condition. Adverse events that have a clear alternative explanation, or transient (\leq 72 hours) abnormal laboratory values without associated clinically significant signs or symptoms may be exempt from dose-reduction rules. Dose interruptions/delays are permitted in the case of medical/surgical events or logistical reasons not related to study therapy (e.g., elective surgery, unrelated medical events, subject vacation, and/or holidays). Subjects should be placed back on study therapy within 4 weeks (28 days) of the scheduled interruption/delay. The reason for interruption/delay should be documented in the subject's study record.

Table 4: Rules for Interruption and Restarting of Study Drug

NCI CTCAE v5.0 Grade/Severity	Timing for Restarting Treatment	Dose Level for Restarting Treatment	Treatment Discontinuation
1-2 (mild-moderate)	Continue treatment at the discretion of the investigator.	N/A	N/A
3 (severe)	Toxicity resolves to Grade 0-1.	Reduce by 1 dose level. ^a	Toxicity does not resolve within 4 weeks (28 days) of last dose, except by approval of the medical monitor. or Second occurrence of previously resolved Grade 3 AE.
4 (life-threatening)	Permanently discontinue.	N/A	Permanently discontinue.

Note: Permanently discontinue for any severe or Grade 3 AE that recurs or any life-threatening event.

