c **For Phase 1b and Phase 2 only:** Potential subjects will be consented using short-form ICF prior to pre-screening biopsy to confirm B7-H4⁺ tumor status. Initial review of eligibility criteria will begin and Demographics and Cancer History and Diagnosis must be documented at time of pre-screening. Collection of AEs and Concomitant medications directly related to study procedures will also begin at pre-screening. Subjects confirmed as B7-H4⁺ must be consented a second time, prior to completing the remainder of screening activities for study participation.

d Visit at Day 8 is required for all subjects at Cycles 1 and 5. Visits on Days 2 and 3 are applicable for Phase 1 subjects only.

e Medical history will include relevant medical or surgical treatment within the last 10 years that are considered to be clinically significant by the investigator.

f Any prior medication received up to 30 days before the first dose of study drug and 90 days after the last dose of study drug will be recorded in the eCRF. Please also refer to sections 5.6.2 and 5.6.3 for details on prohibited and restricted medications.

g Comprehensive Physical examinations must be performed by a medically qualified individual such as a licensed physician, physician's assistant, or an advanced registered nurse practitioner, as local law permits. The comprehensive physical examination will include assessment(s) of the following organ or body systems: skin; head, eyes, ears, nose, and throat; thyroid; lungs; cardiovascular system; abdomen (liver, spleen); extremities; and lymph nodes, as well as a brief neurological examination. The screening physical examination should also include a measurement of height. The targeted physical examination will be a symptom-directed evaluation conducted by the investigator or a medically qualified designee. Notable abnormalities that are considered clinically significant in the judgment of the investigator are to be reported as AEs or Medical History (if applicable at Screening).

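### Table 3's combined liver DLT requires ALP <2 × ULN with no baseline term, so a subject admitted with ALP already at 2–5 × ULN cannot meet it while ALP stays there

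*Combined protocol and SAP*

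**What the plan says.** **The criterion.** The General row of Table 3 (Section 5.4.2) has a combined liver criterion with three limbs: ALT above 3 × ULN together with "bilirubin >2 ULN in the absence of alkaline phosphatase (ALP) elevation (<2 ULN". All three are fixed multiples of ULN. A sub-bullet withdraws the DLT if another cause explains the combination, preexisting liver disease among them. Neither Section 5.4.2 nor any other section gives a baseline-adjusted version.

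**Who may enter.** Criterion 2e of Section 4.2 makes an allowance, "Patients with documented liver or bone metastases: alkaline phosphatase", of up to 5 × ULN. It also admits subjects with liver metastases at AST or ALT up to 5 × ULN. Criterion 2f excludes total bilirubin of 1.5 × ULN or more, except that subjects with Gilbert's syndrome "with elevated total bilirubin may be permitted to enroll after consultation with the medical monitor".

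**Other routes to a DLT.** Table 3 also counts nonhematologic toxicity from Grade 3, certain Grade 3 and all Grade 4 immune-related events, and "Inability to receive the planned number of doses within the 28-day DLT period due to toxicity, regardless of grade". None of these depends on ALP.

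**Dosing.** Section 3.1: "Phase 1 of the study will begin with 14-day cycles". For Grade 1–2 events Table 4 says "Continue treatment at the discretion of the investigator", and Section 5.4.6 adds "Treatment with study drug may be delayed allowing for resolution of toxicity".

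**The concern.** The same liver change is scored differently according to where ALP stood before the first dose. In a subject with normal ALP, a new rise of ALT and bilirubin past the two cut-offs is a DLT unless another cause is found. In a subject who entered at ALP 3 × ULN and stayed there, it is not a DLT under this row.

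This row is the only liver criterion in Table 3 that is not tied to a grade or to missed dosing. What it adds is the combined rise below Grade 3, and that is what these subjects lose. With bone metastases, the raised ALP that switches the row off may have nothing to do with the liver.

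This is a first-in-human study. The Phase 1a escalation rule and the Phase 1b rule of fewer than 3 in 10 are both stated as DLT counts in small cohorts.

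**Working it through.** No power or error rate is involved, so the check is of thresholds, timing and decision rules.

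**1. The logic of the row.** It is met only if ALT >3, bilirubin >2 and ALP <2 all hold (multiples of ULN).

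| Subject | ALT | Bilirubin | ALP | Row met? |
|---|---|---|---|---|
| Entry ALP 3, unchanged | 4 (yes) | 2.5 (yes) | 3 (no) | No |
| ALP 1.5 | 4 (yes) | 2.5 (yes) | 1.5 (yes) | Yes, unless otherwise explained |

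The ALP limb fails at every value from 2 to 5 × ULN, including exactly 2, because the inequality is strict.

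**2. Is the event new?** Bilirubin at entry is below 1.5 × ULN, Gilbert's syndrome aside. Passing 2 × ULN needs a rise of more than 2 − 1.5 = 0.5 × ULN, or more than 2 / 1.5 = 1.33-fold. It is a change since screening.

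**3. Does the missed-dose row catch it?** With 14-day cycles the planned doses in the window fall on Day 1 and Day 15; the third falls on Day 29, outside it. Counting Cycle 1 Day 1 as Day 1, dose 2 can be given as late as Day 28, a delay of 28 − 15 = 13 days, without tripping that row. Table 8 (footnote c) requires pre-dose results to be judged acceptable but states no liver cut-off.

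**4. When would the rise be seen?** Table 7, footnote d: "Visit at Day 8 is required for all subjects at Cycles 1 and 5". On the nominal schedule, post-dose chemistry inside the window is drawn on:
- Day 8;
- Day 15, before dose 2 (the 72-hour allowance lets it be drawn from Day 12);
- Days 26–28, if the Cycle 3 sample is taken ahead of Day 29.

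That is 2–3 scheduled draws, plus any unscheduled ones.

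**5. What one uncounted event changes** (Sections 3.1.1.1 and 3.1.1.2).

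| True count | Recorded count | Decision on true count | Decision on recorded count |
|---|---|---|---|
| 1/3 | 0/3 | Expand to 6 | Escalate |
| 2/6 = 33.3% | 1/6 = 16.7% | MTD exceeded | Escalate |
| 3/10 | 2/10 | Not deemed safe | Deemed safe |

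**6. Would relaxing ALP alone be enough?** No. Take entry at ALT 4, ALP 4 and bilirubin 1.4 × ULN. If only bilirubin moves, to 2.1, a row with the ALP limb waived and ALT still fixed at >3 is met by bilirubin alone (2.1 / 1.4 = 1.5-fold). Requiring ALT of at least 2 × baseline (2 × 4 = 8 × ULN) prevents this.

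**The case against.** The strongest case against the point is that several conditions must coincide: entry ALP of at least 2 × ULN that stays there, a new rise in both ALT and bilirubin, both below Grade 3, no other cause, and dose 2 still given by Day 28. Section 5.4.9 requires permanent discontinuation for a related event that the investigator or medical monitor judges contrary to the subject's interest. Stopping for that reason before dose 2 trips the missed-dose row at any grade and any ALP. So an investigator would have to re-dose despite an unexplained combined rise. That argument stands, and it is why the gap is narrow. It does not close the gap, because re-dosing is permitted.

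The cohort calls (Sections 5.4.5 and 8.7) review all safety data and agree on escalation, and Section 5.4.2 allows a lower MTD to be set later. This also stands: the event is visible and can be weighed. But Section 5.4.5 names only high-grade events for adjudication as dose-limiting, so review does not by itself make the event count.

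For liver metastases, the attribution sub-bullet may already remove the event, so the ALP limb is often not decisive. This is accepted, and it makes bone metastases the cleaner example.

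Section 1.2.3 reports no clinical chemistry effect in the repeat-dose monkey study, and the human tissues it lists with membrane staining do not include liver. This lowers the prior concern without bearing on how the row is worded.

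An ALP limb also has a legitimate use in screening out cholestatic patterns. The fix keeps that use.

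**Conclusion.** The point holds as a minor design weakness. Section 4.2 admits subjects for whom this one criterion cannot be met while ALP stays at 2–5 × ULN, and no other provision makes a combined rise below Grade 3 count when dosing goes ahead.

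Two stronger readings are not supported. A reader might infer that such a subject cannot have a hepatic DLT at all. The Grade 3, immune-related and missed-dose routes remain open, so that is wrong. A reader might also infer a material chance of unsafe escalation. The documents give neither the share of subjects entering with ALP of at least 2 × ULN nor an event rate, and they do not print the Grade 3 laboratory cut-offs. No probability can be calculated, and the decision changes shown above are possibilities under the rules only.

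The conclusion assumes 14-day cycles on the nominal schedule and entry bilirubin below 1.5 × ULN. The reference in the sub-bullet to preexisting liver disease could be worded more clearly but is not a fault in itself.

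**What to change.** At the next amendment, add two sentences to the combined liver criterion in Table 3:

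1. For subjects with Cycle 1 Day 1 ALP ≥2 × ULN, treat the ALP limb as met unless ALP has risen materially over the subject's own baseline. The sponsor sets the threshold; 1.5 × baseline is a suggestion and has no source in the documents. For entry ALP of 2–5 × ULN it gives a ceiling of 1.5 × 2 = 3 to 1.5 × 5 = 7.5 × ULN.
2. Where baseline ALT is already raised, for example above 3 × ULN, also require a material ALT rise, for example to at least 2 × baseline. State whether this covers only the subjects in sentence 1. If it does, the row is unchanged for everyone else.

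Keep the attribution sub-bullet as it stands.

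The cost is small. Section 6 (Tables 8 and 9) already requires chemistry including ALP and ALT at screening and before dosing on Cycle 1 Day 1, so no new procedure is needed. The downside is a few more events to adjudicate. Some may prove to be disease progression or cholestasis, and a misattributed one could turn 0/3 into 1/3 or 1/6 into 2/6 and hold up escalation.

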5.4.3 Management of Dose-Limiting Toxicities or Other Urgent Situations

In all cases, investigators may employ any measures or concomitant medications, after discussion with the medical monitor (whenever possible), necessary to optimally treat the subject.

5.4.4 Follow-Up of Dose-Limiting Toxicities

Any DLT should be followed until it resolves to baseline or appears to have stabilized for a minimum of 4 weeks (e.g., 28 days). During follow-up, subjects should be seen as often as medically indicated to assure safety.

5.4.5 Procedures for Cohort Review and Dose Escalation

Telephone conferences will be scheduled by the sponsor, or sponsor's delegate, with study investigators to review cohort-specific data and overall safety data, to agree on dose escalation, adjudicate individual high-grade AEs as potentially dose-limiting, and guide other major study decisions.

5.4.6 Criteria and Procedures for Dose Interruptions and Adjustments of Study Drug

Treatment with study drug may be delayed allowing for resolution of toxicity. Subjects may resume treatment if no medical condition or other circumstance exists that, in the opinion of the investigator, would make the subject unsuitable for further participation in the study. For toxicities that occur outside of the 28-day DLT period, the treating investigator should contact the medical monitor to discuss the case of any subject whose treatment has been delayed for more than 4 weeks (28 days). **Note:** Patients who have >28-day treatment delay must discontinue from further treatment.

Instructions for dose modifications and interruptions are outlined in Table 4. Individual decisions regarding dose interruptions and reductions should be made using appropriate clinical judgment in consultation with the medical monitor, considering relatedness of the AE to the study drug and the subject's underlying condition. Adverse events that have a clear alternative explanation, or transient (\leq 72 hours) abnormal laboratory values without associated clinically significant signs or symptoms may be exempt from dose-reduction rules. Dose interruptions/delays are permitted in the case of medical/surgical events or logistical reasons not related to study therapy (e.g., elective surgery, unrelated medical events, subject vacation, and/or holidays). Subjects should be placed back on study therapy within 4 weeks (28 days) of the scheduled interruption/delay. The reason for interruption/delay should be documented in the subject's study record.

Table 4: Rules for Interruption and Restarting of Study Drug

NCI CTCAE v5.0 Grade/Severity	Timing for Restarting Treatment	Dose Level for Restarting Treatment	Treatment Discontinuation
1-2 (mild-moderate)	Continue treatment at the discretion of the investigator.	N/A	N/A
3 (severe)	Toxicity resolves to Grade 0-1.	Reduce by 1 dose level. ^a	Toxicity does not resolve within 4 weeks (28 days) of last dose, except by approval of the medical monitor. or Second occurrence of previously resolved Grade 3 AE.
4 (life-threatening)	Permanently discontinue.	N/A	Permanently discontinue.

Note: Permanently discontinue for any severe or Grade 3 AE that recurs or any life-threatening event.

^aNo more than 2 dose reductions of study drug are permitted (see [Table 2](#)). Subjects should be permanently discontinued from study drug if they have AEs requiring more than 2 dose reductions of study drug.

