3.1.2 Phase 2 – Dose Expansion

Phase 2 of the study will further evaluate the safety, tolerability, preliminary efficacy, PK, and pharmacologic activity of the RP2D of NC762 in subjects with advanced or metastatic non-small cell lung (squamous cell), hepatocellular carcinoma, HER2+ breast, and ovarian cancer, or other tumor identified based upon emerging data. Each cohort will be comprised of an individual tumor type. Biopsies at pre-screening and on treatment will be required of all enrolled Phase 2 subjects. During Phase 2 Dose Expansion, subjects with CLIA validated B7-H4+ staining on the membrane of tumor cells confirmed by tumor biopsies will be considered eligible to enroll.

A Simon 2-stage design will be utilized with a stopping rule to allow for early termination of a particular cohort at the end of Stage 1 if there are insufficient responses observed. During Stage 1, 12 evaluable subjects will be enrolled in each cohort; if no responses are observed within the cohort then the cohort will be discontinued. If at least 1 response is observed, 12 additional evaluable subjects will be enrolled in the cohort (Stage 2), for at least 24 evaluable subjects per cohort.

Subjects will continue to receive NC762 at the RP2D and schedule until protocol-defined withdrawal criteria are met. Continuous evaluation of toxicity events will be performed throughout enrollment in Phase 2 of the study. If the cumulative incidence of DLTs occurs in $\geq 33\%$ of subjects after 6 subjects have been observed for at least 28 days, further enrollment may be interrupted until the sponsor has determined the appropriate course of action. All AEs, regardless of the time of occurrence on study may be considered in determining the appropriate dose, schedule, and MNTD.

Toxicity will continue to be monitored throughout the treatment period. If > 33% of subjects (minimum of 6 subjects) experience a \geq Grade 3 toxicity related to study drug after completing \geq 4 cycles, then the MNTD will be determined in conjunction with the investigators and sponsor based on all available safety data.

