5.5 Withdrawal of Subjects from Study Drug

5.5.1 Withdrawal Criteria

A subject may choose to withdraw from the study at any time or be withdrawn from the study by the investigator or sponsor, if the subject is noncompliant with the study requirements. Subjects may also be withdrawn at the discretion of the US FDA or health authorities. If a subject is withdrawn, then every reasonable effort should be made to determine the reason for withdrawal, and this information should be recorded in the electronic case report form (eCRF).

Subjects must be withdrawn from study drug for the following reasons:

- The subject becomes pregnant
- Consent is withdrawn
- Further participation would be injurious to the subject's health or well being
- The subject is lost to follow-up
- Toxicity ([Section 5.4.9](#)). Subjects with unacceptable toxicities must be withdrawn from study drug but will continue to be followed during the safety follow-up visits as specified in [Section 6.4](#)
- The study is terminated by the IRB or regulatory authority

- The study is terminated by the sponsor

A subject may be discontinued from study drug as follows:

- Confirmed radiographic progression of disease per mRECIST v1.1.
- If, during the course of the study, a subject is found not to have met eligibility criteria (see Section 4), then the medical monitor, in collaboration with the investigator, will determine whether the subject should be withdrawn from the study.
- If a subject is noncompliant with study procedures or study drug administration in the investigator's opinion, then the sponsor should be consulted for instruction on handling the subject.

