8.7 Data Monitoring Committee

A Data Monitoring Committee (DMC) will be established for this open-label study. For Phase 1, the sponsor in conjunction with the study medical monitor and CRO will conduct telephone conferences with investigators in order to review cohort-specific data, overall safety data from prior cohorts (if applicable), and to agree on dose escalation, de-escalation, and cohort expansion decisions on a regular basis. For Phase 2, a formal DMC will be organized and comprised of the following members including but not limited to: a chairperson, two non-participating physicians specializing in oncology, the study medical monitor, a non-voting biostatistician, and representatives of the Sponsor and CRO. The committee will meet on a regular basis to review safety and tolerability throughout the study. Additional information on the DMC will be detailed in the DMC Charter.

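### Two safety stop rules do not match across sections: the Phase 2 text omits the MNTD dosing stop, and Table 4 restarts Grade 3 events that Tables 5 and 6 discontinue

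*Combined protocol and SAP*

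**What the plan says.** **MNTD stop.** The trigger is the same everywhere: more than 33% of subjects, with a minimum of 6, have a drug-related toxicity of Grade 3 or higher after at least four cycles. In Table 3 (5.4.2) the consequence is "then dose administration will be stopped, and the MNTD will be determined in conjunction with the investigators and sponsor". The Phase 1a text (3.1.1.1 and the synopsis) says the same. In 3.1.2 and the Phase 2 synopsis the consequence is only "then the MNTD will be determined in conjunction with the investigators and sponsor based on all available safety data". Both Phase 2 texts also say "Subjects will continue to receive NC762 at the RP2D and schedule until protocol-defined withdrawal criteria are met". Section 5.5.1 opens its mandatory list with "Subjects must be withdrawn from study drug for the following reasons". The list covers unacceptable toxicity by reference to 5.4.9 ("Subjects with unacceptable toxicities must be withdrawn from study drug") but has no MNTD entry. Section 8.7 adds oversight: "For Phase 2, a formal DMC will be organized and comprised of the following members".

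**Grade 3 events.** Table 4 labels Grade 3 as severe. It allows restart one dose level lower once the event has resolved to Grade 0-1, with no exception by type of event. The Grade 3-4 row of Table 5 (5.4.7), also labelled severe, says the drug should be stopped permanently for irAEs that are severe or clinically significant, or when steroids cannot be tapered below 7.5 mg/day. The text introduces Table 5 as suggested care. Table 6 (5.4.8) stops the drug permanently after a Grade 3 or 4 infusion reaction. Section 5.4.9 names only ocular irAEs of Grade 2 or higher, plus a judgement-based stop for related events and a 28-day delay limit.

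**28-day limits.** Table 4 ends treatment if "Toxicity does not resolve within 4 weeks (28 days) of last dose, except by approval of the medical monitor". The Note in 5.4.6 says "Patients who have >28-day treatment delay must discontinue from further treatment".

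**The concern.** This is a first-in-human trial with up to 120 Phase 2 subjects, and safety and tolerability are the primary objective. If two operative sections lead to different actions for the same event, sites may treat like subjects differently.

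A site that follows 3.1.2 and 5.5.1 finds no instruction to stop when the MNTD trigger is met; a site that follows Table 3 does. A site that follows Table 4 alone could re-dose a subject after a Grade 3 infusion reaction or a recovered Grade 3 irAE, where another table says to stop. At stake are continued exposure and the consistency of the data on dose reductions and discontinuations due to adverse events.

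**Working it through.** The plan states no figure for these rules, so the check is mainly a comparison of texts, followed by two short calculations.

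**1. MNTD stop**

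- Table 3: its MTD entry separates Phase 1 from Phase 2, but its MNTD entry does not. It applies for as long as subjects are treated, and dosing stops.
- 3.1.1.1 and synopsis Phase 1a: dosing stops.
- 3.1.2 and synopsis Phase 2: same trigger; the MNTD is determined; nothing is said about stopping.
- 5.5.1: no MNTD entry for either phase.

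So Table 3 on its face covers Phase 2, and the Phase 2 text is incomplete against it. No section says whether the stop would apply to one tumor cohort or to all Phase 2 subjects.

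**2. What the six-subject minimum means.** It can mean at least 6 subjects evaluated or at least 6 affected. The smallest count k with k/n > 0.33 is 2 of 6 (0.333), 4 of 12 (0.333) or 8 of 24 (0.333). If at least 6 must be affected, it is 6 of 6, 6 of 12 or 8 of 24.

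The chance of meeting the trigger at a single look is P(X ≥ k) for X ~ Binomial(n, p). The true late-toxicity rates p are assumed, because the documents give none, and all n subjects are taken to be past cycle 4.

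| n | k | Reading | p = 10% | p = 20% | p = 30% |
|---|---|---|---|---|---|
| 6 | 2 | evaluated | 11.4% | 34.5% | 58.0% |
| 12 | 4 | evaluated | 2.6% | 20.5% | 50.7% |
| 12 | 6 | affected | 0.05% | 1.9% | 11.8% |
| 24 | 8 | both | 0.2% | 8.9% | 43.5% |

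If exactly one third is not meant to count as above 33%, 6 subjects need 3 events (1.6/9.9/25.6%) and 24 need 9 (0.03/3.6/27.5%). The two readings agree for a full cohort of 24 and differ widely at 12, the Stage 1 size. These figures describe how often the trigger fires, not how often the sections disagree.

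**3. Grade 3 events**

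- Recovered Grade 3 infusion reaction: Table 4 restarts one level lower; Table 6 stops permanently.
- Recovered, first-occurrence, non-ocular Grade 3 irAE, off steroids: Table 4 restarts; Table 5 advises a permanent stop if the event counts as severe or clinically significant. Both tables attach the word severe to Grade 3. The specific stops (steroid taper failure, recurrence, non-resolution, ocular event) do not apply to this case, and 5.4.9 leaves it to judgement.

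No section ranks the tables. The size of this part cannot be computed, because the documents give no irAE or infusion-reaction rate.

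**4. The two 28-day limits.** Cycles are 14 days with a ±3-day visit window (Table 7, footnote a).

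- Delay counted from the scheduled dose: the limit falls at 14 + 28 = day 42 after the last dose. Table 4's criterion falls at day 28, so the waiver has 42 − 28 = 14 usable days (days 29 to 42). With the window, the limit is 11 + 28 = day 39 to 17 + 28 = day 45, leaving 11 to 17 days.
- Delay counted from the last dose: both limits fall at day 28 and the waiver has 0 usable days. On this reading a dose given on time would already be 14 days late.

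Section 5.4.6 counts non-toxicity delays from the scheduled interruption or delay, which favours the first reading.

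**The case against.** **Silence is not contradiction.** Table 3's MNTD entry has no phase limit, so the natural reading is that its stop covers Phase 2 and that 3.1.2 merely shortens the rule. The 5.5.1 list mainly concerns individual withdrawal, and the MNTD stop is missing there for Phase 1 too. This stands as far as it goes. A reader might infer that the protocol orders dosing to continue after the trigger in Phase 2; the text does not say that. A reader might also infer that nobody could impose the stop. The Phase 2 DMC reviews safety regularly, and what its charter assigns cannot be known because the charter is not in the documents. What remains is an omitted clause beside an instruction to continue.

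**Judgement covers irAEs.** Table 5 is advisory. If every Grade 3-4 irAE were a stop, its steroid-taper clause would be redundant, which suggests a judged subset. Section 5.4.6 requires clinical judgement in consultation with the medical monitor, and 5.4.9 allows a stop for any related event against the subject's interest. So one cannot infer that the protocol requires permanent discontinuation for every Grade 3 irAE. But the shared label severe leaves the meaning open, and the monitor has no stated order between the tables. For infusion reactions, most readers would let the more specific Table 6 govern; Table 4 still has no exception.

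**The 28-day pair.** It is tempting to read Table 4's waiver as overriding the mandatory stop. It does not: it lifts only Table 4's own non-resolution criterion, and the Note and 5.4.9 continue to apply. Contacting the monitor about a delay beyond 28 days is also compatible with stopping. This objection succeeds.

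**Conclusion.** The point holds for two rules. The MNTD dosing stop is stated without phase limit in Table 3 and is missing from both Phase 2 texts. Table 4's general Grade 3 restart is not reconciled with Table 6 for infusion reactions or with Table 5 for irAEs. The infusion-reaction case is the plainer mismatch; the irAE case is an ambiguity about what severe means and which table governs.

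The 28-day delay limit and Table 4's waiver are not in conflict when delay runs from the scheduled dose. That rests on the wording for non-toxicity delays and on 14-day cycles, and the usable days would change under another schedule.

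The consequence is operational: who is re-dosed, how much exposure follows, and how discontinuations are counted. No DLT count, sample size or error rate changes. The trigger frequencies rest on assumed rates and a single look; they show only that the six-subject minimum needs defining. The matter should be fixed because a section read alone could keep dosing, or re-dose, a subject whom another section says to stop.

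**What to change.** 1. In 3.1.2 and the Phase 2 synopsis, add that dosing stops when the MNTD trigger is met, and say whether this applies to the tumor cohort or to all Phase 2 subjects. Wherever the trigger appears, say whether the minimum of six means evaluated or affected.
2. Add one line to Table 4: *For irAEs, Table 5 and 5.4.9 take precedence; for infusion reactions, Table 6 takes precedence.*
3. State in Table 5 whether severe means every Grade 3 irAE. Without this the precedence line leaves the ambiguity in place. The choice belongs to the sponsor's clinicians.
4. Optional: define in 5.4.6 that a toxicity delay is counted from the scheduled dose.

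The edits are short, but they alter dosing and restart rules. Under 11.5 the likely route is a protocol amendment with investigator signature and IRB/IEC approval, and a consent revision if its statements are affected; notifying sites would not be enough. There may be a few more discontinuations. Sample size, visit schedule and analysis stay as they are.
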